8.4. Withdrawal Criteria/Study Discontinuation

Patients may withdraw from the study at any time without stating a reason and without prejudice to further treatment. The Investigator may withdraw a subject from the study and discontinue study treatment and assessments at any time due to safety concerns. Full skin examination will be performed at each visit. If ZORBLISA causes any significant rash that has not occurred previously in the subject, the Investigator should consider discontinuing the subject. In addition, if lesions appear to significantly worsen above the normal cycle seen in the patient, with use of ZORBLISA, the investigator should consider discontinuing the subject.

Early discontinuation of any subject who has given informed consent /assent to participate will be recorded including the reason for discontinuation. The primary reason for a subject withdrawing prematurely will be selected from the following standard categories of early discontinuations.

- 1. Adverse Event and Adverse Reactions: Clinical events occurred that are reported that in the medical judgment of the investigator are grounds for discontinuation in the best interests of the subject.
- 2. Withdrawal of Consent: The subject desired to withdraw from further participation in the study. The subject is not obligated to provide any reason for withdrawal of consent, but where a reason is given this will be recorded on the eCRF.
- 3. Protocol Violation: The subject failed to adhere to the protocol requirements, at the investigator's discretion.
- 4. Lost to Follow-Up: The subject stopped coming for visits and study personnel were unable to contact the subject.
- 5. Other: The subject was terminated for a reason other than those listed above, such as, termination of study by Sponsor.

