14.3. Analysis Considerations

In general, results will be summarized using descriptive statistics. Summary statistics to be used include proportion of patients with complete closure of their target lesion at each visit, mean and standard deviation of BSAI compared with baseline at each visit, and incidence rates of specific adverse events.

Additional evaluations may be made to compare responses of patients in this extension study with their responses in SD-005. For those patients randomized to ZORBLISA in SD-005, the use of summary statistics as described in the previous paragraph will provide an understanding of the long term effect of ZORBLISA in these patients. For those patients randomized to the control arm in SD-005, summary statistics will be used to compare their response to ZORBLISA in SD-006 with their response to control in SD-005.

In addition to the evaluations described above for the primary efficacy and safety variables, secondary and exploratory variables will also be evaluated using summary statistics.

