5.2. Changes from the Analyses Planned in the Protocol/CIP

Subgroup analysis deleted from efficacy analyses. Safety analysis limited to age subgroups.

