6.3. Baseline Definition and Assessments

6.3.1. Baseline definition

For most cases, the baseline visit (Visit 1) will occur at Visit 5 for SD-005. Exceptions are detailed below.

The Body Surface Area Index (BSAI) assessments of lesional skin and wound burden performed at the Visit 5 for SD-005 will be utilized as the baseline assessment for SD-006 unless Visit 1 is ≥ 14 days after the final SD-005 visit in which case the assessment will be repeated.

The urine pregnancy test performed at the final visit for SD-005 will be utilized for entry (Visit 1) into SD-006 only if the visits occur on the same day, otherwise, urine pregnancy test will be performed at Visit 1 as baseline assessment for SD-006.

The physical examination performed at the final visit for SD-005 will be utilized as the baseline assessment for SD-006 unless Visit 1 is ≥ 14 days after the final SD-005 visit, in which case a physical examination will be repeated and used as baseline assessment for SD-006.

The ARANZ picture that documents target wound status at the final visit for SD-005 will be utilized to determine target wound area unless Visit 1 is ≥ 14 days after the final SD-005 visit, in which case the assessment will be repeated on the same wound. For target wounds that are not closed by the end of Study SD-005, the ARANZ picture and calculation of target wound area at the final visit for Study SD-005 will be used as the baseline area size of the target wound for SD-006. The wounds that are closed at the end of study SD-005 will not be followed up and analyzed.

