7. STATISTICAL METHODS

7.1. General Methodology

The final analysis after the study completion will be preceded by at least one interim analysis.

Data will be summarized by treatment groups (based on 005 study treatment: Placebo → SD-101-6.0 and SD-101-6.0 → SD-101-6.0) and overall (where appropriate). Summary and analysis tables will include number of patients (n), mean, standard deviation, median, minimum, and maximum values for all continuous variables. When appropriate, two-sided 95% confidence intervals may be used.

In summary tables of categorical variables counts and percentages will be presented. The denominator for each percentage will be the number of patients within the population (unless otherwise specified).

All analyses for efficacy will be performed using the Intent-To-Treat (ITT) population, all safety analyses will be performed using the safety population. No comparison between treatment groups will be performed. The comparison to baseline will be done by visit in Placebo → SD-101-6.0 group. All hypothesis testing will be two-sided. P-values less than 0.001 will be reported as <0.001 in summary tables.

All statistical analysis will be performed using SAS[®] v9.2 or higher.

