8.6. Analysis of Efficacy Parameters

8.6.1. Analysis of BSAI

No comparison between treatment groups will be performed. The comparison to baseline will be done by visit in Placebo → SD-101-6.0 group using the paired t-test.

- Change in extent of lesional skin based on BSAI at each visit compared to baseline.

To evaluate post-baseline BSAI of lesional skin, both change from baseline and percentage change from baseline will be explored using descriptive statistics. Change from baseline will be calculated as the post-baseline measurement minus the baseline value. Percentage change from baseline will be calculated as the change from baseline divided by the baseline value times 100.

Graphs of the mean change and mean percentage change from baseline over time will also be presented.

- Change in total wound burden based on BSAI at each visit compared to baseline.

This assessment will be analyzed using the same approach for lesional skin as the total body wound burden to both change from baseline and the percentage change from baseline.

Graphs of the mean change and mean percentage change from baseline over time will also be presented.

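### The SAP narrows the protocol's comparison of drug response with control response to before-after paired t-tests in former-placebo patients, and declares neither the narrowing nor the added tests

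*SAP*

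**What the plan says.** **Protocol 14.3 (Analysis Considerations).** The paragraph opens permissively: "Additional evaluations may be made to compare responses of patients in this extension study with their responses in SD-005". For patients randomized to control it then becomes definite: "summary statistics will be used to compare their response to ZORBLISA in SD-006 with their response to control in SD-005". The tool is summary statistics; no hypothesis test is planned.

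**SAP 8.6.1 (Analysis of BSAI).** "No comparison between treatment groups will be performed". Then: "The comparison to baseline will be done by visit in Placebo → SD-101-6.0 group using the paired t-test". Change and percentage change from the SD-006 baseline are also described and graphed, for lesional skin and for wound burden. SAP 7.1 repeats the plan for the former-placebo group and adds "All hypothesis testing will be two-sided".

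**SAP 6.3.1 (Baseline definition).** The BSAI assessments "performed at the Visit 5 for SD-005 will be utilized as the baseline assessment for SD-006", unless Visit 1 falls 14 days or more after the final SD-005 visit, in which case they are repeated.

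**SAP 5.2 (Changes from the planned analyses).** The whole entry reads: "Subgroup analysis deleted from efficacy analyses. Safety analysis limited to age subgroups".

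**The concern.** In Protocol 14.3 the BSAI summaries are expressed relative to baseline, so the natural reading of a patient's response is a change. Comparing the response on drug with the response on control then needs two changes per patient: one over SD-005 and one over SD-006. The SAP computes only the second.

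An uncontrolled change can arise without any drug effect. Protocol 8.4 recognises that lesions fluctuate, in the phrase "if lesions appear to significantly worsen above the normal cycle seen in the patient". Protocol 10.6 leaves concomitant treatment to the investigator. BSAI is scored by a study physician who knows that every patient is on active cream. If former-placebo patients were already improving on control and went on improving at the same rate, the paired t-tests would tend to be significant, and nothing in the SAP's tables would show the earlier trend.

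The stake is the interpretation of a secondary objective. The primary objective is safety and is not touched.

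**Working it through.** **1. The documents side by side**

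| Item | Protocol 14.3 | SAP 7.1, 8.6.1 |
|---|---|---|
| Former-control patients | Response on drug against response on control | Level at each SD-006 visit against SD-006 baseline |
| SD-005 data used | Response during SD-005 | Visit 5 value only, as baseline |
| Tool | Summary statistics | Summary statistics plus paired t-test by visit |
| Declared in SAP 5.2 | n/a | No; only subgroup changes are listed |

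There are two departures: the SD-005 change is missing, and hypothesis tests have been added. With 17 post-baseline visits and two BSAI measures, the added tests number 17 × 2 = 34.

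**2. Inputs for an illustration**

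The plan has no figure to reproduce. About 150 is a roll-over count, not a powered sample size, and the documents give no number of former-placebo patients, no SD, no drift and no alpha. Assumed here: two-sided alpha 0.05, zero drug effect, and n of 75, 50 or 20 former-placebo patients. Drift is expressed as d, in SDs of the paired difference.

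**3. Probability that one visit's paired t-test is significant with no drug effect**

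The test statistic is noncentral t with n − 1 degrees of freedom and noncentrality d√n. For n=75 and d=0.3, noncentrality = 0.3 × 8.660 = 2.598, against a critical value of 1.993, which gives 0.73.

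| d | n=75 | n=50 | n=20 |
|---|---|---|---|
| 0.1 | 0.14 | 0.11 | 0.07 |
| 0.2 | 0.40 | 0.28 | 0.14 |
| 0.3 | 0.73 | 0.55 | 0.25 |
| 0.5 | 0.99 | 0.93 | 0.57 |

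In BSAI points, if the SD of change were 10 and n=75, drifts of 1, 2 and 3 points are d = 0.1, 0.2 and 0.3, so 0.14, 0.40 and 0.73. With n=60 and SD 12 the same drifts give 0.10, 0.25 and 0.48. With n=75 and SD 8 they give 0.19, 0.57 and 0.89.

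**4. What setting change against change would and would not repair**

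Take three values per patient: Y0 at the start of SD-005, Y1 at its end (also the SD-006 baseline) and Y2 at an SD-006 visit. The SAP tests Y2 − Y1. The change-versus-change contrast is (Y2 − Y1) − (Y1 − Y0) = Y2 − 2Y1 + Y0. A simulation of 10,000 trials per case, with zero drug effect and correlation 0.6 between values, gave these rejection rates at n=75 (n=50 in brackets):

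| Non-drug shift of 0.3 | Before-after test | Change versus change |
|---|---|---|
| Equal drift in both periods | 73% (55%) | 5% (5%) |
| Only at the move to open label | 72% (55%) | 31% (23%) |
| Only during SD-005 | 5% (5%) | 32% (23%) |

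A hand check agrees. With equal variances and equal correlation ρ, the paired difference has variance 2(1 − ρ)σ² and the contrast has (1 + 4 + 1)(1 − ρ)σ² = 6(1 − ρ)σ². The contrast's SD is therefore √3 times larger. A 0.3 shift becomes 0.3/√3 = 0.173, with noncentrality 0.173 × 8.660 = 1.50 at n=75 and a rejection probability of 0.32, in line with the simulated 31% and 32%.

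The contrast removes steady drift. It does not remove an open-label effect. It can also mislead where the SAP's test does not, when the shift is confined to SD-005.

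**The case against.** Several stronger readings are tempting, and the documents do not support them.

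- *The SAP uses no placebo-period data and drops the comparison altogether.* It does not. The SD-006 baseline is normally the SD-005 Visit 5 value, and the test is confined to former-placebo patients, so a reduced form survives: level on drug against level at the end of control.
- *The protocol firmly committed to a specific analysis.* Its paragraph opens with a permissive sentence, promises only description, and defines neither a response measure nor an interval. The definite sentence about control patients stands, but a paired difference with a confidence interval goes further than it requires.
- *Barring between-group comparison is itself a departure.* Protocol 14.3 plans no such comparison, and SAP 7.1 already summarises both roll-over groups.
- *The data form a crossover that could isolate the drug effect.* There is one fixed order and an unblinded second period, so period and treatment remain confounded whatever the analysis.
- *Patients opted in when their disease was bad.* Nothing in the documents says so; entry rests on completing SD-005 on study drug.

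The strongest remaining objection is that confounding belongs to the open-label design and that the extra table cures little of it. Much of this stands. SD-005 had a minimum target wound size at entry (Protocol 5.2), so regression to the mean in that study is plausible. Because Visit 5 normally enters both changes with opposite signs, a chance high value there worsens the apparent control response and flatters the drug response. The table should therefore not lead the efficacy results. The objection does not excuse leaving the SD-005 change unreported or the departures undeclared.

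The SAP also nowhere claims that the t-tests establish a controlled drug effect. A label saying so would cost nothing.

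**Conclusion.** The point holds in a limited form. The response-versus-response description in Protocol 14.3 has been narrowed to change from the end-of-control level, visit-wise hypothesis tests have been added, and SAP 5.2 declares neither. The only efficacy hypothesis tests are uncontrolled before-after tests, and a reader of the planned tables could not tell whether a trend was already present on placebo.

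The documents cannot fix the size of the problem. The range of 0.07 to 0.99 in the first table under the working depends entirely on assumed n and drift, with alpha assumed at 0.05. It shows that a paired t-test detects any real mean change whatever its cause; it is not evidence that drift occurred. A reader might infer that the test has a 73% false-positive rate, or that the extra table would yield a causal estimate. Neither inference is supported.

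One textual assumption: SAP 2 cites protocol amendment 2, version 2, whereas the protocol synopsis is labelled version 3. Both describe 1440 days of treatment, and the wording of 14.3 is taken to be in force.

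This should be corrected, but because efficacy is a secondary objective it does not threaten the trial's main purpose.

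**What to change.** 1. **SAP 8.6.1: add a descriptive table** for Placebo → SD-101-6.0 patients. Show BSAI change over SD-005 (its baseline to Visit 5) beside BSAI change over the SD-006 interval closest in length, with the paired difference and its 95% CI (SAP 7.1 already allows intervals), for lesional skin and for wound burden. Show the SD-101-6.0 → SD-101-6.0 group over the same visits as context. State how patients with a repeated baseline are handled. If the table is not wanted, justify leaving it out.
2. **SAP 8.6.1: label the paired t-tests** exploratory and uncontrolled, with no causal reading.
3. **SAP 5.2: list both departures** from Protocol 14.3, namely the narrowed comparison and the added tests.

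**Cost.** Wording, plus one table for each of the two BSAI measures. It needs SD-005 baseline and Visit 5 BSAI. The documents do not give SD-005's length or BSAI schedule, so data availability and the matching SD-006 visit must be confirmed first. Early SD-006 visits should suffer least from the termination, since SAP 6.4.1 expects limited data at later ones.

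**Downsides.** The comparison removes steady drift only, not the open-label effect or regression to the mean during SD-005. Its interval would be about √3 ≈ 1.7 times as wide as that for the SD-006 change alone, under the equal-correlation assumption above. It may give a less favourable estimate if patients were already improving on placebo. It should be supportive description, neither the lead result nor causal evidence.

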7.3. Handling of Dropouts or Missing Data

Dropout patients will not be replaced in this study. Missing data will not be imputed unless specified otherwise in the following section.

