11.2. Body Surface Area Index (BSAI) of Total Wound Burden

(Check only one box and complete the appropriate sections for each region)

1 Ages 1 month to 7 years

Column 1	Column 2	Column 3	Column 4	Column 5
Region Number	Region Description	Regional BSA % that is affected*	Weighting Factor	Total BSA % that is affected **
1	Head / Neck		x .2	
2	Upper Limbs		x .2	
3	Trunk (includes groin)		x .3	
4	Lower Limbs		x .3	
			TOTAL (BSAI)	

2 Age 8 years or greater

Column 1	Column 2	Column 3	Column 4	Column 5
Region Number	Region Description	Regional BSA % that is affected*	Weighting Factor	Total BSA % that is affected **
1	Head / Neck		x .1	
2	Upper Limbs		x .2	
3	Trunk (includes groin)		x .3	
4	Lower Limbs		x .4	
			TOTAL (BSAI)	

* For each region, enter the % of BSA that is affected with open wounds. Score each region separately from 0% - 100%.

** Multiply the value in column 3 by the factor in column 4. The Total value at the bottom of the table is the sum of Column 5 values for each region.

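### Percentage change in BSAI has no rule for a zero baseline, and its mean, the only percentage statistic graphed, runs too high when baseline BSAI fluctuates

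*SAP*

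**What the plan says.** SAP 8.6.1 defines the individual percentage as follows: "Percentage change from baseline will be calculated as the change from baseline divided by the baseline value times 100". For lesional skin it adds: "Graphs of the mean change and mean percentage change from baseline over time will also be presented". Wound burden is handled by the same approach, with reference "to both change from baseline and the percentage change from baseline", and has its own graphs.

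Three other provisions matter.

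- **Tables.** SAP 7.1: "Summary and analysis tables will include number of patients (n), mean, standard deviation, median, minimum, and maximum values for all continuous variables". The percentage tables will therefore carry a median and an n.
- **Absolute change.** SAP 6.4.1 defines change as the visit value minus the baseline value, and 8.6.1 graphs its mean as well.
- **Missing values.** SAP 7.3: "Missing data will not be imputed unless specified otherwise in the following section". Neither this section nor 8.6.1 says what happens when the baseline is 0.

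**The concern.** A ratio with the patient's own baseline underneath has two weaknesses here.

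First, it cannot be computed at a baseline of 0. If the result is treated as missing and not imputed, those patients disappear from the percentage summary while still counting in the absolute one. The two summaries, and the two graphs, then describe different patients.

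Second, when BSAI varies from visit to visit, a patient caught at a low point at baseline gets a large positive percentage at the next visit, while a patient caught at a high point can lose at most 100%. The mean of the ratios is pulled up by the first kind of patient. Protocol 8.4 recognises that lesions follow a usual cycle within a patient, so some fluctuation is expected, but no size is given.

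BSAI of lesional skin and of wound burden are secondary endpoints, and BSAI is the only efficacy measure analysed in SAP 8.6. At stake is whether the percentage graphs describe the size of change fairly. SAP 6.4.1 expects limited data at later visits, where a single near-zero baseline would weigh more.

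**Working it through.** The plan states no expected BSAI result, so there is no figure to reproduce. All distribution values below are assumptions.

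**1. Can baseline BSAI be 0?** The SAP appendix instructs: "Score each region separately from 0% - 100". The total is a weighted sum of four regions, so 0 is a possible score. Protocol 9.3.2.1 counts only open skin as a wound. Protocol 8.2 sets no minimum BSAI at entry. Baseline is normally SD-005 Visit 5 (SAP 6.3.1), after treatment in that study. SAP 8.4 provides a zero category for target wound size but none for BSAI. The formula gives 2/0 for a patient going from 0 to 2, and 0/0 for one who stays at 0.

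**2. Effect of dropping zero baselines (illustration).** Take 150 patients. Those with a non-zero baseline go from 8.0 to 7.5, and those at zero go from 0 to 1.0. The percentage summary shows -0.5/8.0 = -6.25% whatever the share at zero. The mean absolute change over all patients is:

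- 10% at zero: (135 × -0.5 + 15 × 1.0)/150 = -0.35
- 20% at zero: (120 × -0.5 + 30 × 1.0)/150 = -0.20
- 40% at zero: (90 × -0.5 + 60 × 1.0)/150 = +0.10

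This error favours improvement.

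**3. Bias of the mean among baselines above 0.** Let baseline X and follow-up Y be log-normal with the same log-SD s and log-scale correlation r, and let k be the true ratio of means. The variance of log(Y/X) is 2s²(1 - r), so

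expected mean percentage change = 100 × [k × exp(s²(1 - r)) - 1].

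Under the same model the median individual change and the percentage change of the means both equal 100 × (k - 1).

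| s | r | s²(1 - r) | No change (k = 1) | 20% fall (k = 0.8) |
|---|---|---|---|---|
| 0.8 | 0.9 | 0.064 | +6.6% | -14.7% |
| 0.5 | 0.7 | 0.075 | +7.8% | -13.8% |
| 1.0 | 0.9 | 0.100 | +10.5% | -11.6% |
| 0.8 | 0.7 | 0.192 | +21.2% | -3.1% |
| 1.0 | 0.8 | 0.200 | +22.1% | -2.3% |
| 1.0 | 0.7 | 0.300 | +35.0% | +8.0% |
| 1.0 | 0.5 | 0.500 | +64.9% | +31.9% |

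For a 20% fall the expected sign reverses only if s²(1 - r) > ln(1/0.8) = 0.223.

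**4. Simulation check.** Assumptions: median BSAI 8%, between-patient log-SD 1.0, independent visit-to-visit log-SD v (so v² plays the part of s²(1 - r)), values rounded to 0.1 and capped at 100, zero baselines dropped, 3000 runs, true 20% fall. The last two columns give the probability that mean absolute change is negative while mean percentage change is positive.

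| v | Expected mean % | n = 150 | n = 75 |
|---|---|---|---|
| 0.2 | -16.7% | 0.000 | 0.000 |
| 0.3 | -12.5% | 0.000 | 0.005 |
| 0.5 | +2.7% | 0.635 | 0.580 |
| 0.7 | +30.6% | 0.971 | 0.864 |

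At n = 150 the average median percentage change stayed between -19.2% and -19.9%.

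**5. When there is no bias.** If baseline carries no visit-to-visit variation and the percentage change is independent of baseline, a simulated 20% fall gave a mean of -20.0%, against -20.1% for the change of the means.

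**6. The arithmetic in four invented patients.** Baseline to follow-up: 20 to 10, 15 to 9, 10 to 7, 1 to 3. The percentages are -50, -40, -30 and +200, with mean +20%. Mean absolute change is (-10 - 6 - 3 + 2)/4 = -4.25 points. The median percentage is -35%, and the change of the means is 7.25/11.5 - 1 = -37%.

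**The case against.** Much of the protection is already planned. Absolute change is the defined measure in SAP 6.4.1, and Protocol 14.3 names the mean and SD of BSAI against baseline and no percentage. The percentage tables will show the median, the n, and a maximum that exposes extreme values. The study is open-label with safety as its primary objective, and the BSAI changes are explored descriptively. All this stands and keeps the point modest. It does not reach the percentage graphs, which plot means only, and it supplies no rule for a zero baseline.

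Changing the statistic is also partly a choice of estimand. The percentage change of the group mean gives more weight to patients with larger BSAI, and it matches the true value above because the model gives every patient the same expected ratio. That stands too, and is a reason to offer the median as an alternative.

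A reader might infer more than the documents support:

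- **That the graphs will show the wrong direction.** Reversal needs fluctuation above the threshold in step 3, and the documents do not quantify it. The -100% limit alone creates no bias; if no patient changes, every percentage is 0.
- **That the net bias is towards worsening.** Dropped zero baselines pull the other way.
- **That zero baselines occur.** They are permitted, but nothing shows that any patient has one. The log-normal model cannot produce an exact 0 and says nothing about their frequency.
- **That the percentage curve is a headline result.** The SAP presents it beside the absolute graph and ties no decision to it.
- **That the significance test is affected.** SAP 8.6.1 says: "The comparison to baseline will be done by visit in Placebo → SD-101-6.0 group using the paired t-test". It names no scale, so the documents do not show that percentages would be tested.

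**Conclusion.** The point holds in a limited form. The formula is undefined at a baseline the scale allows, and the SAP has no rule for it. Among baselines above 0, the mean percentage overstates the change (a fall looks smaller, or becomes a rise) whenever baseline BSAI fluctuates between visits. Over the assumed range from s = 0.8, r = 0.9 to s = 1.0, r = 0.5, the expected mean is +7% to +65% with no true change and -14.7% to +31.9% with a true 20% fall. Understatement of benefit is the general result under this model; reversal of sign is conditional. With zero baselines dropped, the net direction is unknown.

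The size rests entirely on the assumed log-normal form, s and r. The absence of a zero-baseline rule, and the use of means alone in the percentage graphs, follow from the documents themselves. The change is worth making because it is cheap. Nothing here touches the primary safety objective.

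**What to change.** Amend SAP 8.6.1, for lesional skin and wound burden alike:

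- Keep absolute change as the main summary.
- In the percentage graphs, replace the mean with the median individual percentage change among patients with baseline above 0. Alternatively, use the percentage change of the group mean, 100 × (mean at visit - mean at baseline)/mean at baseline in the same patients, with a note that it weights larger BSAI more heavily. The latter stays defined when some baselines are 0.
- State that individual percentage change is not calculated at baseline 0, and report at each visit the number of such patients and their absolute change.

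A bootstrap confidence interval is optional. The cost is SAP wording, one changed statistic in the graphs and a little programming; no new data are needed.
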